## Abbreviations

AE	Adverse event
aNGT	Adapted nominal group technique
BAPM	British Association of Perinatal Medicine
BDA	British Dietetic Society
BLISS	Neonatal parent charity for preterm infants
COIN	Council of International Neonatal Nurses
CRF	Case report form
CTU	Clinical Trials Unit
EN	Enteral Nutrition
ESPNIC	European Society of Pediatric and Neonatal Intensive Care
ESPR	European Society of Pediatric Research
GCP	Good Clinical Practice
GRV	Gastric Residual Volume
HCPs	Healthcare Professionals
HQIP	Health Quality Improvement Program
HRA	Health Research Authority Health Research Authority Confidential Advisory group
HTA	Health Technology Assessment
ISOC	Independent Study oversight committee
jENS	Joint European Neonatal Societies
NEC	Necrotising enterocolitis
NIHR	National Institute for Health Research
NGT	Naso-gastric tube
NHS	National Health Service
NHS HRA CAG	National Health Service Health Research Authority Confidential Advisory Group

NICU	Neonatal Intensive care unit
NNRD	National Neonatal Research Database
NNU	National Neonatal Units
PICANet	Paediatric Intensive Care Audit Network
PICS	Paediatric Intensive Care Society
PICU	Paediatric intensive care unit
PIM2	Paediatric Index of Mortality version 2
PIS	Participant Information Sheet
PN	Parenteral Nutrition
PPI	Patient and Public Involvement
RCPCH	Royal College of Pediatrics and Child Health
RCT	Randomised clinical trial
REC	Research Ethics Committee
SMG	Study Management Group
SOP	Standard Operating Procedure
UK	United Kingdom
UKNC	United Kingdom Neonatal Collaborative
VAP	Ventilator Associated Pneumonia
WFPICS	World Federation of Pediatric Intensive care Societies

## Protocol Summary

Title:	A Feasibility Study of routine Gastric residual volume measurement in mechanically ventilated Infants and Children
Short Title/acronym	GASTRIC Feasibility Study
IRAS number	244006
REC number	Not for REC review, HRA only. University Ethics Approval number
Sponsor name & reference	UHB
Funder name & reference	NIHR HTA (16/94/02)
ISRCTN no	ISRCTN42110505
Design	Mixed methods study
Overall aim	To determine if a study of not measuring GRV routinely is feasible in UK PICUs and NNUs
Anticipated study duration	18 months

## Background

Underfeeding and inadequate nutrition remain constant concerns in neonatal (NNUs) and paediatric intensive care units (PICUs). An international study of 800 children in 31 PICUs showed only 37% of children received their prescribed energy intake, and that it took nearly 12 days to achieve 90% of their calorie target [1]. On average, children in PICUs receive less than half of their predicted energy requirements [2,3]. Achieving adequate nutrition in preterm infants is vital but equally challenging for different reasons. Whilst extremely preterm infants are routinely commenced on parenteral nutrition (PN) to meet their energy, carbohydrate, protein and lipid requirements, this comes with risks. PN requires invasive intravenous catheters and PN is the ideal medium for bacterial growth - the longer the PN duration, the higher the risk of developing severe infections [4,5]. UK data shows that for babies born at 24 weeks, the median time taken to establish enteral feeding is 19 days (NNRD 2017). Delays in starting and establishing adequate nutrition via the enteral route are known to increase the risk of infectious complications and possibly death [6,7]. Interventions to safely reduce the time to full enteral feeds therefore offer significant health and economic benefits and savings from reduced reliance on costly intravenous feeding.

Inadequate energy delivery to critically ill infants and children has deleterious consequences. There is evidence that malnutrition is prevalent in mechanically ventilated children on admission to PICUs worldwide [8] and that this is linked to worse patient outcomes [9,10], and longer length of mechanical ventilation and intensive care stay [11-14]. There is also evidence in preterm infants that neonatal nutritional status can affect outcomes; negative effects on brain development is an especially worrying consequence of inadequate nutrition [15-17]. A common nursing practice to assess enteral nutrition (EN) 'tolerance' is to measure gastric residual volume (GRV) frequently and routinely [18-21]. GRV is known to be a significant factor in the decision to stop or withhold enteral nutrition [21-24]. Indeed, 'high' GRV often leads to withholding EN and this is a common barrier to delivering adequate amounts of EN in NNUs and PICUs, [22-25].

Despite the prevalence of this practice, the evidence for GRV actually reflecting feed tolerance is poor, and GRV does not correlate directly to enteral feeding tolerance [26-30]. GRV is frequently inaccurate due to position of the feeding tube in the stomach, patient position, feeding method, technique of aspiration and tube and syringe sizes used. What volume constitutes an 'acceptable' level of GRV also remains unknown. So, not only is GRV unreliable as a procedure, but it is also a

time consuming, taking up valuable nursing time and resources (increasing costs) which may be best spent on other patient related tasks [30].

The practice of GRV measurement is widespread in PICUs and NNUs internationally [18,20,21], but with increasing evidence questioning the practice it is now timely to examine this practice in critically ill neonates and children. The measurement of GRV features heavily in efforts to mitigate the perceived risk of pulmonary aspiration in mechanically ventilated patients [26], this risk remains unquantified [32]. In adult intensive care trials, accepting a higher GRV (500ml compared to 200ml)[33] or not measuring GRV at all [32,34] did not adversely affect patient outcomes of ventilator associated pneumonia(VAP) or gastrointestinal complications, however did it improve the achievement of energy goals. A further study showed that just by measuring GRV the risk of delivering inadequate energy increased by 38%. [35]. A before and after study showed that not measuring GRV in 233 preterm infants <34 weeks gestation, resulted in a shorter time to achievement of full enteral feeds with no greater incidence of NEC [36]. So, increasingly, this routine practice is being challenged in NICU, PICUs and across critical care generally [37,38,39]. Despite GRV being routinely measured in all UK and Irish PICUs [18] it is not standard practice, in many French PICUs and NNUs. Our team conducted a pilot study conducted in 2015-2016 to compare practices and outcomes in a UK PICU which routinely measures GRV to a French PICU that does not. We found no significant difference in VAP or adverse events, and a trend towards more consistent achievement of target caloric goals as PICU length of stay increased [38]. In conclusion, a distinct lack of evidence exists to support the traditional, time-consuming routine GRV monitoring as part of enteral feeding protocols in both infants and children. Therefore, there is an urgent need to determine whether it is possible to conduct a trial of routine GRV measurement compared to no GRV in critically ill infants and children.

### **Aims and objectives**

The GASTRIC feasibility study will meet the commissioning brief by the HTA, to answer the question: Is it feasible to conduct a study identifying the impact of not measuring gastric residual volume on clinical outcomes in mechanically ventilated infants and children receiving enteral feeding? To achieve this our specific study objectives are to:

1. Undertake a literature review to identify key outcome measures used for trials of enteral feeding in the PICU and NICU population

[figure not shown]
2. To establish 'standard care practices' around enteral feeding and GRV measurement in all UK PICUs and NNUs (via an e-survey)
3. To explore healthcare professionals (nurses, doctors and dietitians) views around GRV measurement, acceptability of not measuring GRV, alternative methods to assess feed tolerance, willingness to randomise to or comply with a future trial, barriers to recruitment, perceived training needs and inclusion and exclusion criteria
4. To explore PICU and NICU parents and/or patients views around GRV measurement, acceptability of not measuring GRV, willingness to agree to a future trial, barriers to recruitment, patient (parent) centred outcomes and information needs for parents
5. To determine and gain consensus on future trial issues including optimal trial design, primary and secondary outcome measures and inclusion and exclusion criteria.
6. To determine trial feasibility (in both PICU and NICU) using routinely collected national clinical data sets (PICANet and NNRD) and inform sample size calculations for a future trial.
7. To agree (using a consensus process) a standard (control) arm (with routine GRV measurement) and an intervention arm (no routine GRV measurement) of a future trial.
8. To integrate all the data generated and achieve the aim of the feasibility study to determine whether a trial of no GRV measurement is feasible in UK PICUs and NNUs

## **Study design**

A mixed method study involving 5 linked work packages, running in two parallel arms, one in NICU and one in PICU (See Study Flowchart) over an 18-month time frame (below Figure 1).

# GASTRIC Study Flowchart

Figure 1

**Target population:** PICU and NICU clinicians (nurses, doctors, and dietitians), trialists and PICU and NICU parents and/or past patients if appropriate.

**Setting/context:** 190 NNUs and 27 PICUs across the UK

### **Sampling and data collection:**

A literature review of all studies (adult, neonates and children) involving GRV measurement as an intervention in critically ill patients was completed in January 2018. It has critically appraised and summarised detailed data relating to study designs, inclusion and exclusion criteria used, primary and secondary outcome measures used are summarised separately for PICU and NICU. This information will provide important background information for the e-Delphi study, which aims to achieve consensus on trial issues.

## **Work Package 1 – Surveys to establish standard practice**

Work package 1 will involve an electronic survey to all UK PICUs and NNUs to establish ‘standard care practices’ around enteral feeding and GRV measurement. We will conduct this through our national research networks, thus our sample size is 27 UK PICUs [Paediatric Intensive Care Audit Network, PICANet 2016] and 190 NNUs [National Neonatal Research Database NNRD] in the UK. LT (PICU) and NICU (JD) will lead this phase.

**Research aim:** The aim of the e-surveys is to establish what ‘standard’ practice is around GRV measurement in UK PICUs and NNUs.

**Specific objective:** To describe current unit (PICU and NICU) practices around the measurement of gastric residual volume

**Method:** A cross-sectional electronic survey across will be sent to all UK PICUs (n=27) and NNUs (n=190) using our established networks (sent on a link within an email). Our target response rate is >70% and to maximise our response rate we will send three reminders a week apart to these lead individuals. This method has been successful in previous work to generate optimal response rates.

**Sample:** We will ask the lead nurse, consultant and dietitian (or other designated nutrition focussed leads – if not the lead consultant and nurse) to collaboratively complete these surveys based on what their current practice is. We will also request they send any written guidance their unit has around enteral feeding to us. We require only one survey returned per unit and require a unit name/identifier only so we can identify non-responders and target them to maximise our response rate.

**Instrument development:** No previous survey instrument captures the data we need, thus we have developed a survey instrument for NICU and one for PICU. As per best practice in survey design, we will test these instruments for clarity and face validity on 10 individuals (nurses, doctors and

dietitian, who will not be involved in the true survey). The instrument will then be input into electronic software (RedCap) and checked for accuracy again with five separate individuals. We will try to reduce free text within the instrument, but will allow for comments. Each unit will be identifiable and we will ask the units to send any written feeding guidance they have to us. LT has undertaken some pilot work eliciting PICU nurses' views around GRV measurement in a single UK PICU [30] and this work has proven valuable, as there was confusion amongst nurses around the term GRV, which we will now clarify in this national survey.

**Data collection** We will conduct this through our national research networks, thus our sample size is 27 UK PICUs [Paediatric Intensive Care Audit Network, PICANet 2016] and 190 NNUs [National Neonatal Research Database NNRD] in the UK. LT (PICU) and NICU (JD) will lead this phase with assistance from the CTU.

**Data analysis** Data from this survey will be analysed descriptively, as is the intention of this survey. Inferential analysis is not required. Data will be exported from Redcap software in a CSV file format into Microsoft Excel where a summary of standard practice will be produced for a) NICU and b) PICU. This will form the basis for the proposed 'standard arm' of a future trial, to be agreed at the consensus meeting.

## **Work Package 2 – interviews and focus groups involving parents and healthcare professionals**

Work package 2 is a qualitative study involving semi-structured interviews (telephone or face to face) with parents (of children who have experience of mechanical ventilation in a PICU or NICU) and focus groups with NICU and PICU practitioners (nurses, doctors and dietitians). KW will lead this phase.

Interviews will explore parents' views on:

- acceptability of the proposed trial;
- potential barriers to recruitment;
- participant information;
- whether they would be happy to consent for their child's participation in the trial; and
- potential patient-centred outcome measures.

Interviews and focus groups will explore healthcare professional's views on:

- acceptability of the trial including the proposed inclusion and exclusion criteria and clinical equipoise;
- acceptability of not measuring GRV and other measures used to assess feeding tolerance;
- willingness to randomise to a future trial; potential barriers to recruitment consent; and
- associated training needs.

*Inclusion criteria:*

- parents/carers of children with experience of ventilation in both NICU and in PICU in the last three years
- Practitioners (nurses, doctors and dietitians) working in NICU and PICUs

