**Recruitment and sampling**

*Parents*

Based on previous relevant studies we aim recruit 20-30 parents (n= 10-15 in each setting) depending upon point of data saturation. This is when the major themes identified in new data are reoccurring from previous participants/ transcripts and no new major themes are being discovered.

We will recruit parents through three recruitment routes including: 1) social media or website adverts targeting charities and parent support groups (e.g. BLISS, Sepsis Trust, hospital charities); and 2) emails to our national contacts, including the PICANET Families group and if anticipated recruitment rates are low then 3) a advert in a local and/or national newspaper.

The RA will contact gatekeepers (e.g. charity leads/Chief Executive Officers) of support groups for parents whose children may have had experience of ventilation in both NICU and in PICU. The RA will ask them to post the GASTRIC advert on the support group's website and/or social media pages (e.g. Facebook and Twitter). If recruitment is poor, we may also place an advert in local and/or national newspapers. All adverts will include study information and contact details for parents to register their interest in taking part. A link to the study twitter site @GASTRICStudy and the GASTRIC website will enable parents to access further information including the full PIS.

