### **Arranging interviews and focus groups**

#### *Parent interviews*

The GASTRIC RA will respond to parents' requests to participate by email or telephone (depending on which contact details are provided). The researcher will check eligibility. Where parents meet the eligibility criteria, the researcher will arrange a convenient time and date for the telephone or home (in North West England only) interview. A copy of the GASTRIC Study Parent Information Sheet (PIS) which includes a list of proposed GASTRIC outcomes will be sent to parents via email or post (whichever is preferred). Parents will be asked to read this PIS and outcomes list before the scheduled interview. Parents who do not meet the eligibility criteria, or register after the target sample size (10-15 in each setting depending upon data saturation point) has been reached, will be thanked for their time and will take no further part in the study.

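### The parent inclusion criterion in Work Package 2 asks for ventilation in both NICU and PICU, which contradicts the work package's own description and its per-setting sample

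*Protocol*

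**What the plan says.** All of the relevant text is in the Protocol.

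- **Description of Work Package 2.** The interviewees are "parents (of children who have experience of mechanical ventilation in a PICU or NICU", so experience of either setting is enough.
- **Inclusion criteria, same section.** The parent criterion is "parents/carers of children with experience of ventilation in both NICU and in PICU in the last three years".
- **Recruitment and sampling, Parents.** The target is "we aim recruit 20-30 parents (n= 10-15 in each setting) depending upon point of data saturation". The same section describes the support groups to be approached as being for "parents whose children may have had experience of ventilation in both NICU and in PICU".
- **Parent interviews.** Eligibility is checked before anything is booked: "Where parents meet the eligibility criteria, the researcher will arrange a convenient time and date". Parents who fail the check, or who "register after the target sample size (10-15 in each setting depending upon data saturation point) has been reached", are thanked and not interviewed.
- **Study design.** The study runs as two parallel arms, one for NICU and one for PICU.

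**The concern.** The description and the criterion are in the same section and define different groups. One needs ventilation in either setting, the other in both. The difference matters because the criterion is what the researcher applies when a parent registers. A researcher who follows the words as written would decline a parent whose child was ventilated only on a neonatal unit, or only in a PICU. The description of the work package includes both of those parents.

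The parent interviews serve objective 4, on parents' views and their willingness to agree to a future trial. They also feed outputs 1 and 2, on feasibility and on acceptability to parents in each setting. If the literal rule were enforced, families with experience of one setting would not be heard. If staff ignored it, they would routinely depart from the written eligibility criteria. Neither is a good position for a study meant to report on NICU and PICU separately.

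**Working it through.** **Step 1: reproduce the stated sample.** The inputs are the per-setting target of 10-15 and the total of 20-30, both from Recruitment and sampling. With two settings and separate parents in each:

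- lower end: 2 × 10 = 20
- upper end: 2 × 15 = 30

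The stated total is reproduced, provided that the NICU parents and the PICU parents are distinct groups.

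**Step 2: apply the criterion literally.** Every eligible parent would then have a child ventilated in both places, and so would belong to both settings. If each parent counts towards both targets, 10-15 parents fill the two of them, and the total is 10-15 rather than 20-30. The split by setting no longer separates anyone. The literal reading therefore does not fit the plan's own sample.

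**Step 3: set the readings side by side.**

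| Place in the Protocol | Either setting | Both settings |
|---|---|---|
| Work Package 2, description | Yes | |
| Work Package 2, parent inclusion criterion | | Yes, as worded |
| Recruitment and sampling, support groups | | Yes, as worded |
| Recruitment and sampling, target per setting | Fits | Does not fit |
| Parent interviews, target per setting | Fits | Does not fit |
| Study design, parallel arms | Fits | Does not fit |

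**Step 4: who would be excluded.** Let f be the share of otherwise eligible parents whose child was ventilated in both settings within the three years. The literal criterion admits f and excludes 1 − f. The Protocol gives no value for f. Purely as assumed values:

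- f = 5%: 1 − 0.05 = 95% excluded
- f = 20%: 1 − 0.20 = 80% excluded
- f = 50%: 1 − 0.50 = 50% excluded

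The direction is certain for any f below 100%, but the size is not known.

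**Step 5: does the rule operate?** Yes. The section on parent interviews makes the booking conditional on eligibility and says what happens to parents who do not qualify.

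**The case against.** The strongest reply is that this is loose drafting and the intention is plain. The next bullet in the same list admits practitioners who work in NICU and PICUs, and nobody would take that to mean that each practitioner must work in both. The parent bullet can be read the same way, as parents drawn from the two settings. Other text supports this. The target population refers to PICU and NICU parents, one named recruitment route is a neonatal charity, and the parent advisory group counts NICU and PICU parents separately. The per-setting target even stands in the same sentence as the rule for turning parents away.

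Most of this stands, and it makes a drafting error the likely cause. It does not remove the contradiction. In the parent criterion, the word *both* attaches to the child's experience of ventilation, and the gatekeeper sentence repeats the construction. That sentence only describes which groups to approach and does not set eligibility, but it does nothing to correct the criterion. Nothing in the Protocol tells the researcher to read the criterion loosely.

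A reader might also infer three stronger things, none of which the documents support:

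- **That most of the intended sample is excluded.** This needs f below 50%, which is plausible but cannot be checked.
- **That the remaining families would be an unusual, long-stay group.** The Protocol says nothing about them.
- **That 10-15 per setting could not be reached.** Recruitment uses charities, parent groups and national contacts, with newspaper adverts as a fallback. On the literal reading, one parent could count towards both targets.

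**Conclusion.** The criterion is wrong as written. It contradicts the description in its own section, the target of 10-15 parents in each setting, and the parallel NICU and PICU arms. Because eligibility is checked and enforced, literal use would exclude every parent whose child was ventilated in only one setting. How large a share that is cannot be stated from the documents.

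This is an inconsistency of wording in an operative rule, and the design itself is sound. The sample is qualitative and sized by data saturation, so no statistical estimate depends on it. The conclusion rests on one assumption: that the researcher applies the criterion as it reads.

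**What to change.** 1. Reword the parent criterion to: *parents/carers of children ventilated in a NICU and/or a PICU in the last three years*.
2. Make the matching change to the sentence on support-group gatekeepers in Recruitment and sampling.
3. Check that the adverts agree. Their text is not in the Protocol, so it is not known whether they need changing.
4. Optionally, state how a parent with experience of both settings counts towards the per-setting targets. In a saturation-based sample such a parent may properly inform both, so this is a matter of clarity and not a requirement.

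The cost is a change of a few words in two places in the Protocol. The target stays at 10-15 per setting and 20-30 in total.

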**Exclusion criteria**

- Unable to speak English.

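### The parent inclusion criterion for the interviews does not match the protocol's own description of the parents: it omits mechanical ventilation and enteral feeding, and says both settings where either is meant

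*Protocol*

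**What the plan says.** Work Package 2 of the protocol describes the parents to be interviewed in two ways. The opening sentence refers to "parents (of children who have experience of mechanical ventilation in a PICU or NICU". The inclusion criterion listed further down the same section asks for "parents/carers of children with experience of ventilation", without the word *mechanical*; in full it reads "parents/carers of children with experience of ventilation in both NICU and in PICU in the last three years". The only exclusion is "Unable to speak English".

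Under Recruitment and sampling, the target is stated as "we aim recruit 20-30 parents (n= 10-15 in each setting) depending upon point of data saturation". Parents come forward in response to adverts and emails. Under Parent interviews, a researcher checks each registrant against the eligibility criteria.

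The study question, under Aims and objectives, concerns "mechanically ventilated infants and children receiving enteral feeding". Objective 4 in the same section asks for parents' views on measuring gastric residual volume (GRV) and on leaving it unmeasured.

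**The concern.** The listed criterion is the text against which a researcher would naturally screen a parent who registers. It differs from the rest of the protocol in three ways: it drops *mechanical*, it says nothing about enteral feeding, and it joins the two settings with *both*.

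The feeding gap matters most. GRV is measured to judge tolerance of enteral feeds, so a parent whose child was never enterally fed has not seen the practice that the future trial would withdraw. Such a parent would still count towards the target and towards saturation.

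Parent acceptability is one of the study's listed deliverables and part of the overall feasibility judgement, and it rests on a small number of interviews. The *both* wording has the opposite effect. Taken at its word, it would turn away most of the parents the study appears to want.

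**Working it through.** No power or sample-size formula applies, because the number of interviews is set by saturation. The check is a comparison of texts plus one piece of arithmetic.

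**Texts side by side**

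| Place in protocol | Type of ventilation | Enteral feeding | Setting |
|---|---|---|---|
| Aims and objectives, study question | Mechanical | Required | Not stated in the question |
| Work Package 2, opening sentence | Mechanical | Not mentioned | PICU or NICU |
| Work Package 2, inclusion criterion | Any | Not mentioned | Both NICU and PICU |
| Recruitment and sampling, target | Not stated | Not mentioned | Each setting separately |

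**Ventilation.** The criterion is looser than the opening sentence. A child supported only non-invasively could pass the criterion and fail the opening sentence.

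**Feeding.** The study question makes enteral feeding part of the population. The opening sentence, the criterion, the exclusion and the recruitment text do not mention it, so nothing in the parent criteria closes this gap. The Background shows that intensive care and enteral feeding do not always coincide: it says that extremely preterm infants routinely start on parenteral nutrition and that a high GRV often leads to feeds being withheld. It does not say how many ventilated children are never enterally fed.

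**Setting.** The stated total is reproduced as follows:

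- lower end: 2 settings × 10 = 20
- upper end: 2 settings × 15 = 30

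This agrees with the plan's 20-30. The sum works only if each parent is counted in one setting. If every eligible parent had a child ventilated in both settings, each could speak to both, and the protocol would need a rule for assigning them. None is given. The target therefore fits *either setting* and does not fit *both*.

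**Weight of one interview.** One parent in a setting's sample is 1/15 = 6.7% to 1/10 = 10% of that sample. This is a count of interviews, not a weight in an estimate, because the analysis is thematic.

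**What cannot be computed.** The protocol gives no proportion of registrants whose child had only non-invasive support, or was never enterally fed, or was ventilated in one setting only. The number of places affected is therefore unknown.

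**The case against.** The strongest reply is that the protocol's intent is clear. The opening sentence of Work Package 2 names mechanical ventilation in either setting, the criterion below it can be read as shorthand, and nothing says that the researcher would ignore the opening sentence when screening. This stands in part. On ventilation and setting the defect is an inconsistency between two sentences, not a missing requirement. It does not answer the feeding gap, because the opening sentence is silent on feeding too.

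A second reply is that most of the listed interview topics concern a hypothetical trial: its acceptability, barriers, information, consent and outcomes. Parents receive written information and a list of outcomes beforehand, so one without tube-feeding experience can still contribute. That is fair for those topics. It is weaker for objective 4, which asks directly about GRV measurement.

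A third reply is that parents also contribute through the advisory group and the consensus meetings, so the interviews are not the only parental evidence. This limits the harm but does not remove the mismatch.

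A reader might go further and infer that parents are taken strictly in order of registration, so that early registrants from one source could fill the sample. The protocol does not say this. Its order-of-registration rule is under Practitioners and governs focus-group places. For parents it says only that those who "register after the target sample size (10-15 in each setting depending upon data saturation point) has been reached, will be thanked for their time". First-come selection is an inference from that sentence, and several recruitment routes are planned.

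**Conclusion.** The point holds as an internal mismatch with a cheap remedy. The parent criterion should agree with the opening sentence of Work Package 2 on ventilation type, with the per-setting target on setting, and with the study question on enteral feeding. At present it agrees with none of them. The feeding omission is the most substantive part, because no other parent criterion or recruitment text corrects it.

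The size is unknown beyond the 6.7% to 10% of a setting's sample that each parent represents. This conclusion assumes that the listed criterion is what the researcher applies at screening. If the opening sentence is applied as well, only the feeding gap remains.

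Two stronger readings are not supported. A reader might infer that families outside the study population could make up a large share of the sample; no figure in the protocol supports any such share. It would also be wrong to say that parents are screened on ventilation alone, since setting, the three-year window and ability to speak English are also specified. Sampling parents for a deliberate mix of characteristics is one accepted qualitative choice, and its absence is not an error.

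**What to change.** Reword the parent inclusion criterion to: parents or carers of children who were mechanically ventilated and received enteral (tube) feeding during a NICU or PICU stay in the last three years. Make the same change from *both* to *either* in the Recruitment and sampling text on support groups, which repeats the phrase. At the eligibility check already planned under Parent interviews, ask about and record mechanical ventilation and enteral feeding.

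The cost is one reworded criterion, one matching edit and two questions at an existing contact. A few registrants may be turned away and recruitment may be slightly slower. Replacing *both* with *or* widens the pool compared with the literal text. The target numbers and the saturation rule need no change.
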